#### **6.1.2.7 Change in Pain Catastrophizing**

The endpoint will be measuring using the Pain Catastrophizing Scale. The analysis population will include subjects who complete the PCS at baseline and at the 6-month follow-up visit. The endpoint will be calculated as a raw difference score as well as relative change reported as a percentage change from baseline.

### **6.1.3 Demographic/Baseline Characteristic and Descriptive Endpoints**

The following descriptive endpoints will be reported:

- Change from baseline to 12, 18, and 24 months post-permanent implant for quality of life measured using the EQ5D questionnaire will be summarized by mean, standard deviation and 95% confidence interval.
- Change of the PCS score from baseline at 3, 12, 18 and 24 months post-permanent implant will be summarized by mean, standard deviation, and 95% confidence interval.

- Change from baseline to 12, 18 and 24 months post-permanent implant for anxiety measured using the STAI will be summarized by mean, standard deviation, and 95% confidence interval.
- Change from baseline to 12, 18 and 24 months post-permanent implant for depression measured using the PHQ9 will be summarized by mean, standard deviation, and 95% confidence interval.
- Change from baseline to 3, 12, 18 and 24 months post-permanent implant for fear avoidance measured using the TSK will be summarized by mean, standard deviation, and 95% confidence interval.
- Change from baseline to 12, 18 and 24 months post-permanent implant for sleep measured using the MOS Sleep Scale will be summarized by mean, standard deviation, and 95% confidence interval.
- Change from baseline to 12, 18 and 24 months post-permanent implant for physical function measured using the PROMIS Physical Function Scale will be summarized by mean, standard deviation, and 95% confidence interval.
- Change from baseline to End of Trial System Evaluation 3, 12, 18, and 24 months post-permanent implant for pain measured using the NRS will be summarized by mean, standard deviation, and 95% confidence interval.
- Demographics and medical history will be reported. The continuous variable(s) will be summarized by mean and standard deviation. The categorical variable(s) will be summarized by frequencies and percentages.
- Patient waveform preference at 3, 6, 12, 18, and 24 months post-permanent implant will be summarized by frequencies and percentages for participants who had multiple waveforms available to choose from.
- Patient satisfaction at End of Trial System Evaluation 3, 6, 12, 18, and 24 months post-permanent implant will be summarized by frequencies and percentages.
- Global improvement of the patient by using the Patient Global Impression of Change at End of Trial System Evaluation 3, 6, 12, 18, and 24 months will be summarized by frequencies and percentages.
- Medication usage measured in decrease in chronic pain related medication intake since baseline at 3, 6, 12, 18, and 24 months post-permanent implant by frequencies and percentages.
- Battery consumption and/or recharging activities at 3, 6, 12, 18, and 24 months will be summarized by frequencies and percentages.
- Stimulation Assessment measured by using the Stimulation Assessment Form at 3, 6, 12, 18, and 24 months post-permanent implant will examine types of perceived stimulation as well as stimulation coverage and intensity.
- Program information including amplitude, pulse width, frequency and electrode configuration will be summarized.
- System information including device type, model number, lot number, and number of leads will be summarized.
- Device, or procedure-related SAEs and non-serious AEs in subjects who receive permanent implant of the SCS stimulation system will be summarized by frequencies and percentages.

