### 3 Device(s) Under Investigation

#### 3.1 Identification and Description of the Devices under investigation

Table 1: Identification of Devices under Investigation

Device Type	Device name	Model/ Type	Description	Investigational or Market Released
Trial System	SJM Invisible Trial System	3599 & 3032	
The SJM Invisible Trial™ System is an external pulse generator (model 3599) with disposable header (model 3032) that connects to, and is compatible with, commercially available SJM trial leads and extensions. It provides electrical stimulation to nerve structures either intraoperatively or post-operatively during a trial system evaluation period. The External Pulse Generator (EPG) can support up to 16 active electrodes.
 
Stimulation settings are wirelessly programmed securely over Bluetooth using the Clinician Programmer and stored on the EPG.
 
Batteries support a 14-day trial system evaluation period and the EPG also supplies diagnostics that can provide the user additional data regarding the neurostimulation trial.
 
A complete description and illustration of use are provided in the External Pulse Generator Clinician's Manual.
	Market Released
Trial System	Multiprogram Trial Stimulator® (MTS) - can only be used for on- the-table trials.	3510	The Multiprogram Trial Stimulator System (MTS) is a programmable device designed to deliver low-intensity electrical impulses to nerve structures in the dorsal aspect of the spinal cord. The system consists of an external stimulator, one or two trial cables, and percutaneous leads. The stimulator is a small, battery-powered, external device that delivers electrical impulses through the trial cable to the implanted lead(s). It contains electronic circuitry that allows the stimulator to be easily programmed with different stimulation settings for versatile pain control therapy.	Market Released

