#### 4.3.3 Demographic/Baseline Characteristic and Descriptive Endpoint(s)

- Change from baseline to 12, 18 and 24 months post-permanent implant for quality of life measured using the EQ5D questionnaire.
- Change from baseline to 3, 12, 18, and 24 months post-permanent implant for pain catastrophizing measured using the PCS.
- Change from baseline to 12, 18 and 24 months post-permanent implant for anxiety measured using the STAI.
- Change from baseline to 12, 18 and 24 months post-permanent implant for depression measured using the PHQ9.
- Change from baseline to 3, 12, 18 and 24 months post-permanent implant for fear avoidance measured using the TSK.
- Change from baseline to 12, 18 and 24 months post-permanent implant for sleep measured using the MOS Sleep Scale.
- Change from baseline to 12, 18 and 24 months post-permanent implant for physical function measured using the PROMIS Physical Function Scale.
- Change from baseline to End of Trial system evaluation 3, 12, 18, and 24 months post-permanent implant in pain assessed by using the NRS.
- Demographics and baseline characteristics.
- Patient waveform preference (if applicable).
- Patient satisfaction at End of Trial system evaluation 3, 6, 12, 18, and 24 months post-permanent implant.
- Global improvement of the patient by using the Patient Global Impression of Change (PGIC) at End of Trial System Evaluation 3, 6, 12, 18, and 24 months.
- Medication usage measured in decrease in chronic pain related medication intake since baseline at 3, 6, 12, 18, and 24 months post-permanent implant.
- Battery consumption and/or recharging activities.
- Stimulation Assessment measured by using the Stimulation Assessment Form at 3, 6, 12, 18, and 24 months post-permanent implant as well as any unscheduled visit where reprogramming occurs.
- Program information including amplitude, pulse width, frequency and electrode configuration.
- System information including device type, model number, serial number and number of leads.
- Proportion of device, or procedure-related Serious Adverse Events (SAE)'s and non-serious adverse events in subjects who receive permanent implant of the SCS system.

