### **5.3.2 Trial System Implant**

(In clinic, prior to permanent implantation, within 3-45 days from Baseline visit)

Subjects must undergo a successful trial system evaluation of the SCS system prior to permanent implantation of the SCS system. It is a requirement that the subjects will be trialed with BurstDR and only a BurstDR program will be provided to, and used by, the subject. In case of an on-the-table trial evaluation (aka all-in-one procedure), the pain mapping can be done with tonic. The trial system evaluation procedure will be conducted according to the national standards and guidelines. The SCS Trial System Evaluation visit will include recording the following:

- Trial System implant and system information
- Adverse Events (if applicable)
- Deviations (if applicable)
- Withdrawal (if applicable)
- Death (if applicable)

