### **5.3.3 End of Trial System Evaluation**

(In clinic, prior to permanent implantation, timing in accordance with physician standard operation procedures)

If the trial system evaluation is unsuccessful, per standard of care, the subject is considered as a trial system failure and must be withdrawn from the study (withdrawal date is the date when the trial system evaluation ended). The End of Trial System Evaluation visit will include recording the following:

- Trial system evaluation conclusion information, patient reported pain relief and patient satisfaction
- Patient Reported Outcome Measures (NRS, PGIC)
- Programming information and program usage including programming parameters record
- Adverse Events (if applicable)
- Deviations (if applicable)
- Withdrawal (if applicable)
- Death (if applicable)

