## 5.9 Subject Withdrawal

Respecting the subject's right to withdraw, the Investigator should make all reasonable efforts to retain the subject in the clinical investigation until completion of the clinical investigation. Subjects must be informed about their right to withdraw from the clinical investigation at any time and for any reason without sanction, penalty or loss of benefits to which the subject is otherwise entitled. Withdrawal from the clinical investigation will not jeopardize their future medical care or relationship with the Investigator. Subjects will be requested to specify the reason for the request to withdraw. Reasons for subject's withdrawal include, but are not limited to:

- Subject refuses to continue participating in the study.
- Subject does not meet the inclusion/exclusion criteria
- Subject is deceased (cause must be documented).
- Subject's non-compliance.
- Subject's participation is terminated by the PI or Investigator, although the subject consented, since participation is no longer medically appropriate.
- Subject is 'lost to follow up': Subject does not adhere to the scheduled follow up visits but has not explicitly requested to be withdrawn from the clinical study (this does not apply to missed visits). Site personnel should at all times make all reasonable efforts to locate and communicate with the subject in order to achieve subject compliance to the scheduled follow up visits.

A subject will be considered 'Lost to Follow-up' after 2 consecutive missed visit(s) and a minimum of two unsuccessful phone calls from investigational site personnel to the subject or contact to schedule the next follow-up visit. These two phone calls must be documented in the subject's hospital records. If the subject is deemed lost to follow-up a letter should be sent to the subject's last known address or to the subject's general practitioner (GP) and a copy of the letter must be maintained in the subject's hospital records. This letter serves as a last attempt to bring the patient back into compliance. If the patient does not return to the hospital for the next study visit within 2 weeks after the letter was sent, the subject shall be considered as withdrawn. The date of withdrawal should be the date of the first missed study visit.

When subject withdrawal from the clinical investigation occurs, the subject should be followed up as part of standard care. The status of the subject's condition should be documented at the time of withdrawal.

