## 7.1 Risks Associated with the Clinical Study Device

### 7.1.1 Anticipated Adverse Device Effects

The use of a neurostimulation system involves risks. In addition to the risks commonly associated with surgery, below are listed the anticipated potential adverse effects with the use of a neurostimulation system:

- Unpleasant sensations or motor disturbances, including involuntary movement, caused by stimulation at high outputs (if either occurs, turn off your EPG/IPG immediately)
- Undesirable changes in stimulation, which may be related to cellular changes in tissue around the electrodes, or changes in electrode position
- Changes in stimulation or reduced pain relief due to loose electrical connections

- Changes in stimulation or reduced pain relief due to lead failure
- Stimulation in unwanted places or chest wall stimulation
- Changes in stimulation or reduced pain relief due to lead migration
- Epidural hemorrhage
- Hematoma
- Infection
- Spinal cord compression
- Paralysis from placement of a lead in the epidural space
- Cerebrospinal fluid (CSF) leakage
- Paralysis below the level of implant
- Weakness, clumsiness and numbness below the level of implant
- Pain below the level of implant
- Persistent pain at the lead site
- Persistent pain at the IPG site
- Seroma (mass or swelling) at the IPG site
- Seroma at the lead incision site
- Allergic or rejection response to device/implant materials
- Implant migration
- Skin erosion around the implant
- Loss of stimulation due to premature battery depletion/battery failure

The St. Jude Medical™ MRI conditional neurostimulation systems are designed to minimize the potential adverse events that may cause patient harm. The following potential adverse events may occur in the MRI environment:

- Lead electrode heating resulting in tissue damage or serious patient injury
- IPG heating resulting in tissue damage in the implant pocket or patient discomfort or both
- Induced currents on leads resulting in overstimulation or shocking sensations
- Damage to the IPG or leads causing the system to fail to deliver stimulation or causing the system to deliver overstimulation
- Damage to the functionality or mechanical integrity of the IPG resulting in the inability to communicate with the IPG
- Movement or vibration of the IPG or leads

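### The only planned adverse-event summary covers permanently implanted subjects, so those who are trialled but never implanted (a projected 72 of 240) enter no pre-specified safety summary

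*Combined protocol and SAP*

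**What the plan says.** The statistical section (6.1.3) gives the safety analysis in one line: "Device, or procedure-related SAEs and non-serious AEs in subjects who receive permanent implant of the SCS stimulation system will be summarized". The endpoint list (4.3.3) has the same restriction, to serious and "non-serious adverse events in subjects who receive permanent implant of the SCS system". No other part of section 6 plans an adverse-event summary.

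The trial system is one of the devices under investigation. Section 3.1 says of the external generator: "It provides electrical stimulation to nerve structures either intraoperatively or post-operatively during a trial system evaluation period". The trial step is compulsory (5.3.2): "Subjects must undergo a successful trial system evaluation of the SCS system prior to permanent implantation of the SCS system". Section 4.1 places the trial evaluation period within the study's purpose. Under 5.3.3 a subject whose trial is unsuccessful leaves the study, and the "withdrawal date is the date when the trial system evaluation ended".

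Collection is wider than analysis. Sections 5.3.2 and 5.3.3 record adverse events at the trial-implant and end-of-trial visits. Section 8.2 starts surveillance at consent and makes all serious events, and all non-serious device effects, reportable to the sponsor.

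**The concern.** Membership of the safety set is decided by something that happens after exposure. A subject has a lead placed and is stimulated by the external generator, and is counted only if the trial leads to a permanent implant. The anticipated effects in 7.1.1 include harms of epidural lead placement, and one entry names the external generator alongside the implanted one ("if either occurs, turn off your EPG/IPG immediately"), so risk does not begin at permanent implant.

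The planned percentage is a valid description of implanted subjects. It cannot describe the risk of starting the pathway with a trial procedure, because some of those exposed are in neither numerator nor denominator. If a complication during the trial stopped a subject from being implanted, that subject would be among those omitted. Section 5.9 allows for withdrawal by the investigator "since participation is no longer medically appropriate", although that route is general and not specific to the trial phase.

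The end-of-trial change in NRS offers a comparison. It is scheduled in 5.3.3 and Table 2 and summarised in 6.1.3 with no stated restriction to implanted subjects. No adverse-event summary has the same reach.

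**Working it through.** **Inputs**, all from section 6.3: 267 enrolled; 10% lost between baseline and trial; 30% trial failure; 14% lost from implant to 6 months; stated results of 168 implanted and 145 at 6 months.

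**Reproducing the plan's figures** (each rate applied to those who remain):

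- Trialled: 267 × (1 − 0.10) = 240.3
- Implanted: 240.3 × (1 − 0.30) = 168.2 (plan: 168)
- At 6 months: 168.2 × (1 − 0.14) = 144.7 (plan: 145)

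Adding the first two losses instead gives 267 × (1 − 0.30 − 0.10) = 160.2 implanted and 160.2 × 0.86 = 137.8 at 6 months. Neither matches, so the plan applies the 30% to subjects who reach the trial.

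**Who falls outside the planned summary:**

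- Enrolled but not implanted: 267 − 168.2 = 98.8
- Never trialled, so not exposed: 267 − 240.3 = 26.7
- Trialled but not implanted: 240.3 × 0.30 = 72.1
- Share of trialled subjects omitted: 72.1 / 240.3 = 30%
- Share of trialled subjects covered: 168.2 / 240.3 = 70%

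**Sensitivity to the failure rate.** The 30% is carried over from an earlier study. Taking 20% and 40% as an assumed range, the omitted group is 240.3 × 0.20 = 48.1 or 240.3 × 0.40 = 96.1.

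**What cannot be computed.** The documents give no adverse-event rate for either phase and do not say how many trial failures follow a complication. No bias in the reported percentage can therefore be calculated, in size or in direction.

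**The case against.** The best defence is that the restriction is a deliberate scope choice. Sections 4.2.1 and 4.2.2 concern subjects with a multiple-waveform neurostimulator, there is no primary or secondary safety objective, the devices are market-released, and 4.3.3 and 6.1.3 agree with each other. This explains the implanted-subject summary and is a reason to keep it. It does not explain having no other, because 4.1 includes the trial period in the study's purpose and 3.1 lists the trial system as a study device.

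Several stronger readings are tempting, and the documents do not support them:

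- *Trial-phase harm goes unsummarised altogether.* The restriction is by subject, not by time. Trial-phase events in subjects later implanted are not excluded by the wording.
- *Events escape collection or oversight.* They do not; sections 5.3.2, 5.3.3 and 8.2 cover both. Nor does the plan forbid a wider table. It only fails to pre-specify one.
- *The 72 include the subjects stopped by complications.* The 72 are trial failures as the plan projects them. Whether a complication that prevents implant counts as a trial failure is not stated.
- *Events in 30% of exposed subjects will be lost.* The 30% is a share of subjects, not of events. How many of them would have an event is unknown.
- *Every end-of-trial benefit is summarised for all trialled subjects while harm is not.* Section 6.1.3 does list "Patient satisfaction at End of Trial System Evaluation" and a global impression of change, and 5.3.3 collects both, but Table 2 marks neither at that visit. Only the NRS change is consistent across the three places, so the comparison should rest on it alone.

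**Conclusion.** The gap is real and is one of analysis, not of data collection. Subjects who undergo the trial-system procedure and are never implanted have no pre-specified safety summary. The projected number is about 72 of 240, on two assumptions: that the planning rates in 6.3 hold, and that nobody is lost between a successful trial and implant, since the plan states no such loss. The effect on any reported adverse-event percentage is unknown. The primary and secondary endpoints are unaffected. The change is worth making because the present rule selects the safety set on a post-exposure outcome and the correction is small.

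**What to change.** Keep the implanted-subject summary. In 4.3.3 and 6.1.3 add one descriptive table of device- or procedure-related serious events and non-serious events, with frequencies and percentages, for all subjects in whom a trial-system procedure was started, whether or not they were later implanted. Specify three details:

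1. For staged trials, count events from the trial procedure to permanent implant or withdrawal.
2. Show on-the-table cases as a separate row or stratum. Section 3.1.1 describes trial and implant as one procedure for these, so a window from trial to implant has almost no length. Report the events of the combined procedure there, without dividing them between trial and implant.
3. State that failed-trial subjects are observed only to their withdrawal date, which 5.3.3 sets at the end of the trial evaluation.

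The cost is wording in two sections and one extra table. The visit schedule already records adverse events at both trial visits, so no new collection appears necessary; the case report forms are held separately (Appendix E) and should be checked to confirm this. The drawback is short follow-up in the non-implanted subjects, which limits what the table can show about later events.

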## **4 Clinical Investigation Design**

### **4.1 Clinical Investigation Design**

The study is designed as a post-market, international, multicenter, interventional, prospective, single-arm study. The purpose of this clinical study is to examine pain relief and other outcomes for subjects with chronic, intractable pain of the trunk and/or limbs who use BurstDR stimulation during the trial evaluation period and at 6, 12, 18 and 24 months after permanent system implant. Furthermore, the study seeks to explore sustainable pain relief, psychological outcomes, and stimulation usage patterns with a device capable of delivering multiple stimulation modes (BurstDR and tonic) through 24 months post-permanent implant. Finally, this study will collect MRI safety information, when available, for enrolled patients.

The investigation will be conducted in approximately 30 centers in EMEA, US, Canada and ANZ. Estimated enrollment duration is approximately 18 months with 24 months follow-up. Approximately 267 subjects will be enrolled in the study. A maximum of 53 subjects can be included per center. The study may continue up to 4 years, dependent on the rate of enrollment (approximately 18 months enrollment + 24 months follow-up + time to close the investigation and provide final report).

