### **8.2 Safety Reporting**

Safety surveillance within this study and the safety reporting both performed by the Investigator and the Sponsor, starts as soon as the subject is enrolled in this study (date of signature of the informed consent).

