## Clinical Investigation Plan

Safety surveillance and the safety reporting will continue until the last investigational visit has been performed, the subject is deceased, the subject/Investigator concludes his participation into the clinical investigation or the subject withdrawal from the clinical investigation.

All adverse event data including deaths will be collected throughout the clinical investigation and will be reported to the Sponsor on a CRF.

Adverse events will be monitored by the Investigator until they are adequately resolved or the subject has ended his/her participation in the trial, whichever comes first. The status of the subject's condition should be documented and reported to the Sponsor at each visit.

Per the CIP, the applicable reportable adverse event data including deaths will be collected throughout the clinical study and will be reported to the Sponsor through the EDC system. The Sponsor will ensure that all applicable events are reported to the relevant authorities as per regulations. The Investigator must notify the IRB/EC, if appropriate, in accordance with national and local laws and regulations, of the AEs reported to the Sponsor.

Reportable events to Sponsor are considered:

- All non-Serious Adverse Device Effects (procedure/device related)
- All Serious Adverse Events (whether or not the event is considered device or procedure related)
- Adverse events related to MRI scan

All the above events will be reported to the Sponsor, as soon as possible, but no later than 3 calendar days from the day the site personnel became aware of the event, or as per the investigative site's local requirements if that requirement is more stringent. The date the site staff became aware that the event met the criteria for an SAE must be recorded in the source documents.

For unexpected failure modes or unexpected adverse events, the site should follow their standard reporting practices for medical device reporting (MDR)/Vigilance reporting for medical devices per the regulations.

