### **8.2.1 Subject Death**

Subject deaths will be documented and reported to the Sponsor on the applicable CRF as soon as possible after becoming aware of the event. It is the Investigator's responsibility to notify the IRB/EC per the IRB/EC policy.

Should death occur, the Investigator is requested to record death information in the hospital records and immediately document the information on the Death CRF and submit to Sponsor through the electronic data capture (EDC) system deployed by Abbott.

- All efforts to obtain the details about the circumstances surrounding the patient death should be made by the Investigator.
- If a death event is an outcome of an adverse event, an AE CRF must be completed in addition to the Death CRF.
- The subject's death is an early conclusion of the subject's participation in the study. Therefore, the Investigator is requested to complete the Withdrawal form.

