## **9 Clinical Data Handling**

The Sponsor will be responsible for the data handling. The Sponsor and/or its affiliates will be responsible for compiling and submitting all required reports to governmental agencies. Data will be analyzed by the Sponsor and may be transferred to the Sponsor's locations worldwide and/or any other worldwide regulatory authority in support of a market-approval application.

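### Every SAE and death is collected from consent, but the only pre-specified safety summary covers related events in permanently implanted subjects; SAEs judged unrelated, all deaths, and events in subjects never permanently implanted have no planned summary.

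*Combined protocol and SAP*

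**What the plan says.** **Collection.** Section 8.2 says that safety surveillance "starts as soon as the subject is enrolled in this study (date of signature of the informed consent"). Its list of reportable events includes "All Serious Adverse Events (whether or not the event is considered device or procedure related") and "All non-Serious Adverse Device Effects (procedure/device related"). Section 8.2.1 adds that "Subject deaths will be documented and reported to the Sponsor on the applicable CRF", with an AE form as well when the death is the outcome of an adverse event.

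**Analysis.** Among the descriptive endpoints in 4.3.3 the only safety item is the "Proportion of device, or procedure-related Serious Adverse Events (SAE)'s and non-serious adverse events in subjects who receive permanent implant" of the SCS system. Section 6.1.3 gives the matching analysis, frequencies and percentages of "Device, or procedure-related SAEs and non-serious AEs in subjects who receive permanent implant of the SCS stimulation system". Nothing else in 4.3 or section 6 plans a safety summary.

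**Setting.** Section 4.1 describes a "post-market, international, multicenter, interventional, prospective, single-arm study". No blinding and no independent event adjudication is described, and no section says who decides whether an event is related. Section 9 states: "Data will be analyzed by the Sponsor".

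**The concern.** The collection rule and the analysis rule do not match. The protocol gathers SAEs without regard to cause and then, in the one place where it says what will be shown, applies two filters: the event must be judged related to device or procedure, and the subject must have received a permanent implant.

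The first filter makes the safety result depend on a causality judgement by someone who knows that the device is in place. If an SAE is classed as unrelated, no planned output shows that it occurred, so a reader cannot judge whether the classification was reasonable. The second filter removes subjects who had leads placed for the trial evaluation and went no further, although that step is itself invasive and their events are reported. What is at stake is how complete and how checkable the safety account is.

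**Working it through.** **Step 1: set collection against planned summary.**

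| Event | Reportable (8.2, 8.2.1) | In the planned summary (4.3.3, 6.1.3) |
|---|---|---|
| Related SAE, permanently implanted subject | Yes | Yes |
| SAE judged unrelated, permanently implanted subject | Yes | No |
| Related non-serious event, permanently implanted subject | Yes | Yes |
| Unrelated non-serious event | Not on the reportable list | No; nothing reportable is lost |
| Death from a related event, permanently implanted subject | Yes | Yes, as a related SAE; no separate death count |
| Any other death | Yes | No |
| Any SAE, related non-serious event or death in a subject never permanently implanted | Yes | No |

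The wording leaves open whether the relatedness qualifier also governs the non-serious events. This does not affect the result: on either reading, unrelated SAEs are filtered out.

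**Step 2: reproduce the plan's projection.** The inputs from section 6.3 are 267 enrolled, 10% attrition between baseline and trial, 30% trial failure, and 14% attrition from permanent implant to 6 months.

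- Reach the trial: 267 × 0.90 = 240.3
- Permanently implanted: 240.3 × 0.70 = 168.2 (plan: 168)
- At 6 months: 168.2 × 0.86 = 144.7 (plan: 145)

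The plan's figures reproduce, so 168 is the projected denominator of the safety summary.

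**Step 3: count the subjects outside that denominator.**

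- Outside the summary: 267 − 168 = 99, and 99 / 267 = 37%
- Leave before the trial: 267 × 0.10 = 26.7
- Reach the trial and fail it: 240.3 × 0.30 = 72.1
- Check: 26.7 + 72.1 = 98.8, or about 99

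The figure of 72 takes everyone who reaches the trial to have a trial implant and, as 6.3 does, allows no loss between a successful trial and permanent implant.

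**Step 4: number of events omitted.** This cannot be derived. The documents give no SAE rate and no share judged related. Purely as an illustration, let p be the proportion of the 168 implanted subjects with an SAE and r the share of those judged related. The subjects left out are then 168 × p × (1 − r). With p = 0.05 and r = 0.75 that is 168 × 0.05 × 0.25 = 2.1. With p = 0.20 and r = 0.25 it is 168 × 0.20 × 0.75 = 25.2. Both p and r are assumptions, and the range from 2 to 25 shows only that the answer is governed by them.

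**The case against.** The case on the other side has several parts.

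- **Deaths are not wholly absent.** A reader might infer that no death would appear in any table. The documents do not support that: Appendix C counts an adverse event that led to death as an SAE, so a related death in a permanently implanted subject enters the planned summary. What is unplanned is a count of all deaths, including those judged unrelated.
- **The plan does not forbid further tables.** A reader might infer that unrelated SAEs will be missing from the final report. Section 6.1.3 states what will be reported and excludes nothing else, so the sponsor could add them. The gap is in pre-specification. Section 15 does not close it, because it commits only to publishing outcomes specified in advance.
- **Causality categories may exist.** Appendix C defines an adverse device effect without grading relatedness, but the case report forms are held separately (Appendix E) and may carry a scale. Section 9.2 already provides an audit trail of changes to entered data. It would be wrong to say that relatedness goes unrecorded or can be altered without trace.
- **An all-cause count has no comparator.** In a single-arm study it cannot show an excess of events, nor does it remove the assessor's knowledge of treatment. This stands. The gain is transparency: readers see what was classed as unrelated.
- **Subjects who fail the trial are observed briefly.** Section 5.3.3 withdraws them when the trial evaluation ends, so few events may arise. That limits the number but gives no reason to leave out an invasive step.
- **Safety is a descriptive endpoint** in a post-market study of market-released devices, and neither the primary nor the secondary objective concerns it. This stands and limits the weight of the point.

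**Conclusion.** The mismatch holds on the text. All SAEs and deaths are collected from consent, and the only pre-specified safety summary is limited to related events in permanently implanted subjects. No summary of SAEs judged unrelated or of all deaths is planned. On the assumptions of 6.3, about 99 of 267 enrolled subjects fall outside the summary, about 72 of them after a failed trial implant. The safety result therefore rests on a relatedness judgement that readers cannot check.

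No number of omitted events is claimed, and nothing in the documents suggests that events have been or will be misclassified. The point is worth correcting because the remedy is cheap. It does not touch the primary NRS analysis or the sample size.

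**What to change.** Amend 4.3.3 and 6.1.3 so that all SAEs and all deaths are tabulated regardless of relationship, broken down by the relationship to device or procedure recorded for each event. Present the table for two populations: all enrolled subjects, which matches the start of collection at consent, and all subjects with a trial implant, which confines it to those exposed to a procedure. Keep the existing table of related events in permanently implanted subjects alongside.

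The cost is one more table, built from data that the protocol already requires, with no added visits or subjects. Headline event counts will rise, because events with no link to the device will be shown. The breakdown by relationship lets a reader see that.
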